### Concomitant Medications

The number and proportion of patients receiving each reported medication will be summarized by Anatomical Therapeutic Chemical (ATC) code (WHO Drug version

December 2014 or beyond) and preferred term for each treatment group as coded by the World Health Organization Drug (WHODRUG) dictionary. A listing of all concomitant medications by patient will also be provided.

### Physical Exam

Complete physical examinations, including a neurological examination, will be performed at Baseline, Weeks 24 and. Brief physical examinations will be performed at Week 8, 16, 32, and 40. The full physical examination results will be reported in a shift table, if appropriate, by examination category. The physical examinations will also be listed.

### Vital Signs

Vital signs are collected every 8 weeks including seated systolic blood pressure and diastolic blood pressure measured in millimeters of mercury (mmHg), heart rate in beats per minute, respiration rate in breaths per minute, and temperature in degrees Celsius (°C). Vital signs measurements will be reported descriptively at each time point.

### Suicidal Ideation and Behavior

Prospective assessment of suicidal ideation and behavior is a regular part of development programs involving any drug being developed for any psychiatric indication, as well as for all antiepileptic drugs and other neurologic drugs with central nervous system activity (FDA Draft Guidance, 2012). The Columbia Suicide Severity Rating Scale (C-SSRS) is a standardized rating instrument used to assess the suicidal ideation and behavior in an at-risk population (Posner et al. 2011). To prospectively assess suicidal ideation and behavior, the C-SSRS will be administered by trained site personnel. The Baseline/Screening C-SSRS will be administered at the Screening and Baseline visits; the Since Last Visit C-SSRS will be administered at all subsequent visits.

Results for all subjects in the safety population will be reported in listing format.

#### **8.9.1 Adverse Events to Monitor**

Appendix 10.6 includes certain adverse events and liver related investigations.

Tables summarizing patient incidence of the following will be generated:

- All AEs;
- SAEs;
- Treatment-related AEs;
- Treatment Related SAEs
- Liver-related Investigations

## 10 APPENDICES

### 10.1 Schedule of Events

ASSESSMENTS AND EVENTS*	SCREENING a	BASELINE a	TREATMENT PERIOD b							SAFETY FOLLOW-UP c	
			-4 to -1	0	4 (TC)	8	16	24	32	40	
WEEK											
INFORMED CONSENT	X										
MEDICAL HISTORY, HEIGHT AND WEIGHT d	X										
DYNAMOMETRY	X	X			X	X	X	X	X	X	
6-MINUTE WALK TEST (6MWT)	X	X			X	X	X	X	X	X	
SIT-TO-STAND TEST	X	X			X	X	X	X	X	X	
WEIGHTED ARM LIFT TEST	X	X			X	X	X	X	X	X	
GNE MYOPATHY FUNCTIONAL ACTIVITIES SCALE (GNEM-FAS)		X			X	X	X	X	X	X	
INDIVIDUAL NEUROMUSCULAR QUALITY OF LIFE QUESTIONNAIRE (INQoL)		X			X	X	X	X	X	X	
CREATINE KINASE		X			X	X	X	X	X	X	
CLINICAL GLOBAL IMPRESSION SCALE (CGI) e		X					X			X	
FREE SERUM SA LEVELS f		X			X	X	X	X	X	X	
FREE, TOTAL AND BOUND URINE SA LEVELS f	X	X			X			X		X	
URINE TEST FOR MANNAC g	X	X			X			X		X	
INTERVAL HISTORY h		X			X	X	X	X	X	X	X
PHYSICAL EXAMINATION	X	X i			X	X	X i	X	X	X i	X
VITAL SIGNS	X	X			X	X	X	X	X	X	X
HEMATOLOGY, CHEMISTRY PANEL, URINALYSIS	X	X			X	X	X	X	X	X	X
PREGNANCY TEST	X	X			X			X		X	X

ASSESSMENTS AND EVENTS*	SCREENING a	BASELINE a	TREATMENT PERIOD b							SAFETY FOLLOW-UP c	
			-4 to -1	0	4 (TC)	8	16	24	32	40	
WEEK											
CONCOMITANT MEDICATIONS	X	X			X	X	X	X	X	X	X
SUICIDAL IDEATION AND BEHAVIOR j	X	X			X	X	X	X	X	X	X
ADVERSE EVENTS	X	X	X b		X	X	X	X	X	X	X
TREATMENT DISPENSED k		X			X	X	X	X	X		
TREATMENT COMPLIANCE					X	X	X	X	X	X	

\* Refer to Study Reference Manual for recommended timing and order of assessments to be administered at each study visit

a Potential subjects will be screened approximately seven days (up to 28 days) before the Baseline Visit. Study drug will be dispensed only after all study procedures at the Baseline Visit have been performed. For subjects who discontinue prior to completing the study, every reasonable effort should be made to perform the Early Termination (ET) procedures within four weeks of discontinuation.

b Visits occur every 8 weeks  $\pm$  5 days; subjects will be contacted by telephone call (TC) at Week 4 for abbreviated safety assessment. Additional unscheduled telephone calls may also occur for subject follow up. Unscheduled visits are allowed for safety or administrative purposes. Notify the medical monitor before an unscheduled visit.

c The Safety Follow-up visit occurs four weeks ( $\pm$  5 days) after a subject receives the last dose of study medication (i.e. Week 52).

d Medical history will include a detailed GNEM disease-specific medical history.

e CGI-Severity scale will be assessed at Baseline (Week 0) along with identification of 3 target areas for disease improvement; CGI-Improvement scale will be assessed at each subsequent visit using 3 target areas identified at Baseline.

f Pre-dose blood samples and first-morning void urine will be collected to assess trough SA levels; record volume of urine collected.

g An aliquot from first morning void urine will be used for assessment of ManNAC; record volume of urine collected.

h Interval history will include any signs, symptoms, or events (i.e. falls) experienced by the subject since the prior study visit that are not related to study procedure(s) performed at prior study visits or study drug. Interval history may include exacerbation or improvement in existing medical conditions (including the clinical manifestations of GNEM) that might interfere with study participation, safety, and/or positively or negatively impact performance of functional assessments.

i The physical examinations at Baseline and Weeks 24 and 48 will be complete, including a neurological examination; all others will be brief physical examinations.

j Baseline/Screening C-SSRS administered at Screening and Baseline visits. Since Last Visit C-SSRS administered at all subsequent visits.

k Subjects should be instructed to return unused study drug and packaging to every visit.

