Rationale: This change was made based on feedback from the sites regarding symptomatic patients who were above the original upper limit of 50 years of age.

2. [Section 7.5.5.6](#) was updated to clarify that leftover biological samples (from the protocol-specified blood and urine requirements) may be used for future research, including but not limited to biomarker research.

Rationale: This change was made to clarify that leftover volume of blood and urine samples may be used for future research purposes.

CLINICAL STUDY PROTOCOL AMENDMENT SUMMARY OF CHANGES AND RATIONALE

UX001-CL301 Amendment 4

25 March 2016

The Protocol UX001-CL301 Amendment 2 (dated 23 September 2015) has been modified by Amendment 3 (Italy) to provide additional rationale on the selection of the endpoints for this study, as requested by Agenzia Italiana del Farmaco (AIFA), and Amendment 4 to harmonize the study protocol with the Italy-country specific amendment, to clarify the frequency of DMC meetings, to clarify the assessments that will be conducted at Screening, to clearly define the safety follow-up call, and to clearly define safety reporting requirements. The major changes to the protocol are summarized below.

1. Synopsis, Data Monitoring Committee (Section 7.6.7), and Review of Safety Data (Section 8.5.5.1) were updated to indicate that DMC meetings will occur at least two times per year instead of quarterly.

Rationale: This change was made to align the meeting frequency between the protocol and the DMC Charter.

2. Schedule of Events (Table 2.1) was updated to remove the Free, Total and Bound Urine SA Levels from the Screening Visit. Drug Concentrations Measurements (Section 7.5.3) was also updated to reflect this change.

Rationale: This change was made to clarify the visits when drug concentration measurements will be conducted. The total volume of the first morning void is needed to calculate Urine SA levels and cannot be assessed at the Screening Visit.

3. Schedule of Events (Table 2.1), Footnote g was updated to clarify how the urine sample for ManNAc testing will be collected. Urine Testing for ManNAc (Section 7.5.4) was also updated to reflect this change.

Rationale: This change was made to clarify that the urine for this test will come from the urinalysis sample, rather than from the first morning void.

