SUICIDAL IDEATION AND BEHAVIOR ^j	X	X		X	X	X	X	X	X	

ASSESSMENTS AND EVENTS*	SCREENING ^a	BASELINE ^a	TREATMENT PERIOD ^b							SAFETY FOLLOW-UP ^c
	WEEK -4 to -1	0	4 (TC)	8	16	24	32	40	48/ET ^a	52 (TC)
ADVERSE EVENTS	X	X	X ^b	X	X	X	X	X	X	X
TREATMENT DISPENSED ^k		X		X	X	X	X	X		
TREATMENT COMPLIANCE				X	X	X	X	X	X	

* Refer to Study Reference Manual for recommended timing and order of assessments to be administered at each study visit

- a. Potential subjects will be screened approximately seven days (up to 28 days) before the Baseline Visit. Study drug will be dispensed only after all study procedures at the Baseline Visit have been performed. For subjects who discontinue prior to completing the study, every reasonable effort should be made to perform the Early Termination (ET) procedures within four weeks of discontinuation.
- b. Visits occur every 8 weeks ± 5 days; subjects will be contacted by telephone call (TC) at Week 4 for abbreviated safety assessment. Additional unscheduled telephone calls may also occur for subject follow up. Unscheduled visits are allowed for safety or administrative purposes. Notify the medical monitor before an unscheduled visit.
- c. To be completed only for subjects who complete the study and choose not to enroll in the extension study, UX001-CL302, or who discontinue the study early. This call is not required for subjects who are eligible and choose to take part in the extension study, UX001-CL302. The site personnel will initiate a safety follow-up telephone call 28 days (+5 days) after a subject's last dose of study drug to collect information on any ongoing or new AEs, serious adverse events (SAEs), and concomitant medications. Appropriate follow-up should continue until all safety concerns, in the Investigator's opinion, are resolved.
- d. Medical history will include a detailed GNEM disease-specific medical history.
- e. CGI-Severity scale will be assessed at Baseline (Week 0) along with identification of 3 target areas for disease improvement; CGI-Improvement scale will be assessed at each subsequent visit using 3 target areas identified at Baseline.
- f. Pre-dose blood samples and first-morning void urine will be collected to assess trough SA levels; record volume of urine collected.
- g. An aliquot from the urine sample provided for the standard urinalysis will be used for assessment of ManNAc.

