7.5.3 Drug Concentration Measurements

The concentration of free SA in serum will be measured. At the Baseline Visit and each subsequent visit a serum sample will be collected prior to the morning dose of study medication (pre-dose) to assess trough levels of free SA.

The free, total, and bound urine SA levels (corrected for creatinine) will be measured. At the Baseline, and Week 16, 32, and 48 (or Early Termination) visits, first-morning void urine will be collected (pre-dose) to assess trough levels; the volume obtained will be recorded.

Collection and processing instructions can be found in the Laboratory Manual.

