7.5.4 Urine Testing for ManNAc

An aliquot from the urine sample provided for the standard urinalysis testing will be analyzed for the presence of ManNAc at Screening, Baseline, and Week 16, 32, and 48 (or Early Termination) visits to detect noncompliance with prohibited medication restrictions.

Collection and processing instructions can be found in the Laboratory Manual.

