#### 8.8.4 Analyses of Sialic Acid, Creatine Kinase and Free ManNAc

The following clinical lab outcomes will be analyzed using GEE using the SA analysis set. No imputation will be performed for missing data. Free, total, and bound urine SA and urine ManNAc are collected at Baseline, Week 24, and Week 48. All other labs are collected every 8 weeks up to Week 48.

- Free SA: Free SA levels in serum assess the drug concentration in the bloodstream resulting from treatment and are the best indicator of compliance with the treatment regimen. Free SA levels in serum are expressed in micrograms of SA per ml of serum
- Free SA in urine: Free SA levels in urine will be assessed to determine the overall absorption of SA-ER over time. Free SA levels in urine will be expressed in micrograms of SA per ml of urine.

- Total SA in urine: Total SA levels in urine will be assessed to determine the accumulated excretion of sialic acid from dosing. Total SA levels in urine will be expressed in micrograms of SA per ml of urine.
- Bound Sialic Acid in urine: Bound SA levels in urine is calculated as the difference between each subject's total sialic acid and free sialic acid in urine corrected for total protein. Bound sialic acid in urine may also be corrected for creatine and calculated as the difference between each subject's total sialic acid and free sialic acid corrected for creatine. The primary correction for SA will be total protein with creatine correction only used when an alternate method is required
- Creatine Kinase Levels: CK levels in serum will be measured to assess the degree of reduction of CK levels observed as a surrogate for muscle injury.
- Free ManNAc in urine: Free ManNAc levels in urine will be assessed to determine the amount of naturally occurring ManNAc in the urine of study subjects and the stability of these levels over time. Free ManNAc levels in urine will be expressed in micrograms of SA per ml of urine. Changes from baseline in Free ManNAc levels in urine will be analyzed.
- Free ManNAc/Free SA in urine: The ratio of free ManNAc to free SA levels in urine will be assessed to ensure compliance with the restriction placed on ManNAc consumption during the study period.

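### SAP and protocol name different urine specimens for ManNAc, so the planned ManNAc/SA ratio would divide concentrations from two specimens unless a site happens to use one void

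*SAP*

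**What the plan says.** **ManNAc specimen.** SAP Section 10.1, footnote g to the schedule of events: "An aliquot from first morning void urine will be used for assessment of ManNAC; record volume of urine collected". Protocol Table 2.1, footnote g: "An aliquot from the urine sample provided for the standard urinalysis will be used for assessment of ManNAc". Protocol Section 7.5.4 agrees with its own table: "An aliquot from the urine sample provided for the standard urinalysis testing will be analyzed for the presence of ManNAc".

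**Urine SA specimen.** Here the documents agree. Protocol Section 7.5.3: "first-morning void urine will be collected (pre-dose) to assess trough levels; the volume obtained will be recorded". SAP Section 10.1, footnote f: "Pre-dose blood samples and first-morning void urine will be collected to assess trough SA levels; record volume of urine collected".

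**Planned use.** SAP Section 8.8.4: "The ratio of free ManNAc to free SA levels in urine will be assessed to ensure compliance with the restriction placed on ManNAc consumption". The same section expresses free urine SA and free urine ManNAc in micrograms per ml, states no dilution correction for either, and plans a change-from-baseline analysis of ManNAc on that scale.

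**Units in the protocol.** Sections 7.5.3, 7.6.4.3 and 7.6.5 all specify urine SA corrected for creatinine.

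**The concern.** A ratio of two urine concentrations is free of hydration effects only when both come from the same specimen. SAP footnotes f and g, read alone, put both analytes in the first-morning void, and the ratio would then be sound in that respect. Under the protocol's collection rule the numerator comes from one sample and the denominator from another, and nothing in SAP Section 8.8.4 adjusts for that.

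What is at stake is how far the ratio can be read as a check on the ManNAc restriction. Protocol Section 7.4.6.1 treats that restriction as essential to interpreting the trial. A ratio that moves with hydration says less about intake than the SAP supposes.

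**Working it through.** The plan gives no figure on this point to reproduce. The check is a side-by-side reading, a short piece of algebra and an illustration under stated assumptions.

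**1. Which rule governs collection.** SAP Section 1 gives the SAP precedence on analysis methods only. SAP Section 4 says data are collected according to the protocol's schedule, and Protocol Section 7.5.1 makes Table 2.1 the primary source for visit procedures. Sites therefore collect as the protocol says.

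**2. Specimens and units that result.**

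| Analyte | Specimen collected (protocol) | Specimen in SAP 10.1 | Scale in SAP 8.8.4 | Scale in protocol |
|---|---|---|---|---|
| Free ManNAc | Urinalysis sample | First-morning void | Per ml | Test for presence |
| Free SA | First-morning void | First-morning void | Per ml | Corrected for creatinine |

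The current protocol text indicates that the two specimens are distinct. Table 2.1 tests ManNAc at Screening, a visit with no urine SA collection, so at that visit at least the ManNAc urine is not the SA void.

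**3. Effect on the ratio.** Let dU and dF be the concentration factors of the urinalysis sample and the first-morning void, and let M and S be the dilution-free levels.

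Observed ratio = (M × dU) / (S × dF) = (M/S) × (dU/dF).

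With one specimen dU = dF and the factor is 1. With two it remains in the ratio.

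The ManNAc change from baseline is M(t) × dU(t) − M(0) × dU(0). It carries the dilution of both visits whichever specimen is used.

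**4. Possible size (assumed inputs).** The documents give no urine variability. Suppose the log concentration factor has SD s in each specimen and correlation ρ between the two. Then

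added log SD = s × √(2(1 − ρ)), and 95% factor = exp(1.96 × added log SD).

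| s | ρ | Added log SD | 95% factor, either way |
|---|---|---|---|
| 0.3 | 0.6 | 0.3 × √0.8 = 0.27 | 1.7 |
| 0.5 | 0.3 | 0.5 × √1.4 = 0.59 | 3.2 |
| 0.7 | 0 | 0.7 × √2 = 0.99 | 7.0 |

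A second parametrisation gives a similar range. For independent lognormal factors with CV 30%, 50% or 70%, the added log SD is √(2 ln(1 + CV²)) = 0.415, 0.668 or 0.893. The 95% factors are 2.26, 3.70 and 5.76.

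**5. Does the protocol's creatinine correction rescue the ratio?** No. SAP Section 8.8.4 states per-ml units and prevails on analysis methods. Even if SA were corrected, the numerator would keep dU. There is a further trap: Table 7.5.5.6.1 marks urinalysis creatinine as relevant to the drug concentration measurements. Dividing first-void SA by urinalysis creatinine would again mix two specimens.

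**The case against.** The strongest reply is that footnote g is a stale line in an appendix. SAP Section 4 already defers to the protocol's schedule, so the footnote changes nothing at the sites. That is right about collection. It does not help the analysis, because protocol collection is exactly what separates the two terms of the ratio.

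A second reply is that separate voids are not mandated. Protocol Section 7.5.5.6 has the urinalysis urine collected before study drug and Section 7.5.3 has the first-morning void collected pre-dose. The urinalysis sample has no stated clock time, and the details sit in a Laboratory Manual that is not among the documents. This stands in part: a site could use one void for both. Nothing requires it, however. The Amendment 4 rationale, used here only as corroboration, treats the two as different: "the urine for this test will come from the urinalysis sample, rather than from the first morning void".

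A third reply is that the ratio is not the only check. This stands. Protocol Section 7.5.4 and SAP Section 4.6 test for ManNAc in its own right, and the ratio appears only in the SAP.

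A reader might go further and infer that true ManNAc use will be missed, or that compliant subjects will be flagged. The documents do not support that. They give no ratio threshold and no subject-level classification; SAP Section 8.8.4 analyses these outcomes by GEE. The Per Protocol set (SAP Section 6.2) depends only on dosing compliance of at least 80%, so the ratio excludes nobody. How the ratio responds to ManNAc intake is not established even within one void: the denominator is the study drug's own analyte, and the protocol regards ManNAc as a source of SA, so intake could raise both terms. Detection or misclassification rates would need a decision rule that the plan does not contain.

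**Conclusion.** The specimen conflict between current SAP and current protocol text is real. As written, the SAP's ManNAc/SA ratio would carry an uncorrected dilution factor wherever a site takes two voids, and the per-ml ManNAc change would carry one regardless. The SAP's per-ml free SA is a second departure from the protocol, which specifies creatinine correction.

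The actual error cannot be computed from the documents. The range of about 1.7-fold to 7-fold rests wholly on the assumed log SDs and correlations and on a lognormal model. It describes spread in individual ratios, not bias in a treatment comparison.

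The consequence is confined to a supportive compliance check. No primary, secondary or tertiary efficacy endpoint, analysis set or decision rule depends on it. Severity: minor.

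**What to change.** 1. Align SAP Section 10.1, footnote g, with the protocol's specimen.
2. In SAP Section 8.8.4, analyse ManNAc per mg creatinine, using creatinine from the same urinalysis sample. Creatinine is already in the urinalysis panel (Protocol Table 7.5.5.6.1).
3. Express free urine SA corrected for creatinine measured in its own first-morning void, as the protocol's analysis sections require. Reconcile this with the SAP wording for bound SA, which makes total protein the primary correction and names creatine, presumably meaning creatinine, as the alternative.
4. Keep a ManNAc/SA ratio only if it is formed from these same-specimen-normalised values or from one shared void. Normalising removes dilution but not any real change between two collection times, so the SAP should state which basis is used.

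While Section 8.8.4 is open, its collection weeks for urine SA and ManNAc (Baseline, 24 and 48) should be reconciled with Protocol Sections 7.5.3 and 7.5.4 (Baseline, 16, 32 and 48, with ManNAc also at Screening).

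Cost: SAP wording and a small programming change, with no new visit or sample. If creatinine is not already measured in the first-morning void, one routine creatinine assay on that urine is needed.

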## 10.2 Missing Observation in Hand Held Dynamometry and GNEM-FAS

Imputation rules outlined in this section for dynamometry are defined below and are based on the distinct pattern of muscle weakness associated with GNE Myopathy and the features of the dynamometers used in this study. The most common cause of missing data is muscle weakness severe enough to prevent the subject from registering the minimum amount of force against the dynamometer required to obtain a measurement during a maximum voluntary isometric contraction maneuver. In those cases, the value is imputed to 0, and preserves the ability to calculate the UEC and LEC scores. There are some scenarios in which non-random missing HHD data values result in missing UEC and LEC values. When strength in a particular muscle group exceeds the resistance that can be applied by the administrator, a reliable value cannot be obtained from the dynamometer. This is a recognized limitation of a hand-held device (Visser et al. 2003). In GNE Myopathy, the only muscle group at risk for this scenario is the knee extensors, due to the relative sparing of the quadriceps. All other non-random missing HHD data are related to the clinical condition of the subject at the time of the testing where a test may not be administered due to pain, injury, contracture or another extenuating circumstance that could cause discomfort to the subject. The proposed plan for the handling of this data is intended to provide the most accurate estimate of muscle strength and physical function possible based on knowledge of the disease and the outcome measures obtained during the conduct of previous studies.

Missing observations in HHD for individual muscle group will be imputed based on reason for missing and if the muscle strength measurement is missing on both sides or one side. The table below provides a summary of the imputation rule followed by detailed descriptions.

Instrument	Missing Reason	Imputation
HHD missing BOTH sides	Too Weak	0
	Too Strong	NA , UE/LE composite not computed
	Pain	NA , UE/LE composite not computed
	Injury	NA , UE/LE composite not computed
	Contracture	NA , UE/LE composite not computed
	Other	NA , UE/LE composite not computed
HHD missing ONE side	Too Weak	0
	All other reasons	The value from the other side that was measured

*Missing Reason = Weakness*

A value of 0 should be imputed for a W.

- If both sides are W, a value of 0 is assigned to each side and the muscle group IS counted as part of the UE or LE composite.
- If one side is W, a value of 0 is assigned to that side and the 0 is averaged with the value from the other side. The muscle group IS counted as part of the UE or LE composite.

*Missing Reason = Contracture*

A value of 0 should NOT be imputed for a C. A C is missing data because the test was not performed due to the contracture.

- If both sides are C (which would be rare), then the data for this muscle group is missing and the UE or LE composite will be set to missing.
- If one side is C, then the data is missing from this side and the value from the other side should be used to reflect the total strength for this muscle group. The muscle group IS counted as part of the UE or LE composite.

*Missing Reason = Pain*

A value of 0 should NOT be imputed for a P. A P is missing data because the test was not performed due to pain.

- If both sides are P, then the data for this muscle group is missing and the UE or LE composite will be set to missing.
- If one side is P, then the data is missing from this side and the value from the other side should be used to reflect the total strength for this muscle group. The muscle group IS counted as part of the UE or LE composite.

*Missing Reason = Injury*

A value of 0 should NOT be imputed for an I. An I is missing data because the test was not performed due to pain.

- If both sides are I, then the data for this muscle group is missing and the UE or LE composite will be set to missing.
- If one side is I, then the data is missing from this side and the value from the other side should be used to reflect the total strength for this muscle group. The muscle group IS counted as part of the UE or LE composite.

*Missing Reason = Too Strong*

An S indicates that the test was attempted but that the subject overpowered the administrator and a valid value could not be obtained.

- If both sides are S, then the data for this muscle group is missing and the UE or LE composite will be set to missing.
- If one side is S, then the data is missing from this side and the value from the other side should be used to reflect the total strength for this muscle group. The muscle group IS counted as part of the UE or LE composite.

*Missing Reason = OTHER*

No value should be imputed if there is an O.

- If both sides are O, then the data for this muscle group is missing and the UE or LE composite will be set to missing.
- If one side is O, then the data is missing from this side and the value from the other side should be used to reflect the total strength for this muscle group. The muscle group IS counted as part of the UE or LE composite.

When an individual question is missing in GNEM-FAS. The average score is calculated for the domain and then multiplied by the number of questions in the domain:

Mobility Subscale Score =  $10 \times \text{Sum(Available Items)} / \text{Number of Available Items}$

Upper Extremity Subscale Score =  $8 \times \text{Sum(Available Items)} / \text{Number of Available Items}$

Self-Care Subscale Score =  $7 \times \text{Sum(Available Items)} / \text{Number of Available Items}$

If a domain has more than 50% (inclusive) items missing ( $\geq 5$  for Mobility,  $\geq 4$  for Upper Extremity,  $\geq 3$  for Self-Care), the domain score will not be calculated. The Total FAS core will only be calculated if all three domain scores are available.

